3.2. PHASE 1 DOSE ESCALATION

The dose escalation portion of the study is based on Design 4 in [Simon 1997](#) and comprises an initial period of accelerated titration cohorts (Stage 1) followed by 3+3 (Rolling 6) cohorts (Stage 2) as illustrated in [Figure 3](#) below. This design is appropriate for cytotoxic therapies to minimize patient dosing at subtherapeutic levels. Additionally, two Phase 1 clinical trials with similar aminoglycoside-modified Dox-based drugs used similar accelerated dosing protocols and dose adjustment criteria ([DiPaola 2002](#); [Schöffski 2017](#)).

Figure 3: Schema of Single Patient Accelerated Dose Escalation Followed by 3+3 Design with Modified Fibonacci Dose Escalation

The SRC (see section 3.2.7 Safety Review Committee) will review all available safety data at the completion of Cycle 1 for each of the dose escalation cohorts and the cohort receiving 20 mL SQL70 biopolymer from Cycle 1 to evaluate possible DLTs, recommend whether more patients should be enrolled at a given dose level / cohort, and recommend whether to dose escalate or to stop enrollment based on the definition of DLTs in addition to its members' best clinical judgement.

3.2.1. Accelerated Titration (Stage 1)

In the absence of AEs considered by the SRC to be clinically relevant during any cycle, the SQP33 protodrug accelerated dose titration stage includes 1 patient enrolled per cohort with a doubling of the SQP33 protodrug dose level between cohorts.

Escalation transitions to a standard 3+3 modified Fibonacci design (see below) upon identification during the DLT period of either:

- a DLT (see section 3.2.6 Dose-Limiting Toxicity), or
- any Grade ≥ 2 AE considered to be at least possibly related to study drug

3.2.2. 3+3 (Rolling 6) Design (Stage 2)

The 3+3 (Rolling 6) design stage includes 3-6 patients enrolled per cohort and utilizes a modified Fibonacci scale to determine the dose level increase and minimum number of patients enrolled per dose level (Table 3). In the Rolling 6 design, a minimum of three, and up to six patients may be concurrently enrolled at each dose level in the study prior to convening the SRC to evaluate the safety and tolerability of the dose level.

The first cohort of patients enrolled in the Stage 2 dose escalation portion will be at the same dose level as the highest evaluated Stage 1 dose level; an example of this is shown in [Figure 3](#). This will ensure that any dose level resulting in a DLT is tested in additional patients prior to continued dose escalation. If 2 patients experience 1 or more DLTs in any cohort, no additional patients will be enrolled at that dose level and further patients will be enrolled at a lower dose level.

Decisions as to whether to allow additional enrollment beyond the minimum of three into a cohort or pause accrual for that cohort will be made by the Sponsor based on available data (i.e., the Sponsor will inform sites if a cohort is still open for additional accrual or if the cohort is closed to accruals). Dose level assignments are based on the number of participants currently enrolled in the cohort, the number of DLTs observed, the number of participants who have not completed the DLT period, general tolerability observed, and any available PK data.

Table 3: Modified Fibonacci Dose Escalation Scale (Stage 2)

Number of Patients with DLTs in a Dose Level	Action
0 patients with DLTs across 3-6 patients in a dose level	Enroll an additional 3 to 6 patients at a dose level escalation of 50%
1 patient with a DLT across 3-5 patients in a dose level	
 Enroll additional patients (for a total of 6 at this dose level) 
 If no patients experience additional DLTs across the 6 total patients, then enroll 3 patients at a dose level escalation of 33% If a second patient experiences a DLT, see the below (≥ 2 DLTs across ≥ 3 patients at a dose level)
≥ 2 patients with DLTs in a dose level	
 Dose escalation will be stopped. 
 An intermediate dose level may be explored that is not higher than the MAD

DLT = dose-limiting toxicity; MAD = maximum administered dose.

3.2.3. Phase 1: 20 mL SQL70 Biopolymer (from Cycle 1) Cohort

During the Phase 1 portion of the study, to evaluate the administration of 20 mL of SQL70 biopolymer in one or two lesions starting at Cycle 1, patients will be enrolled in a separate cohort at an initial dose level of SQP33 protodrug that is lower than the dose level being evaluated in the standard dose escalation at the time of initiation of this cohort. This 20 mL SQL70 biopolymer (from Cycle 1) cohort will follow the same 3+3 (Rolling 6) escalation design and DLT rules with 3-6 patients enrolled in the cohort. A per cohort SRC meeting will convene following the same guidelines as utilized for the SQP33 protodrug escalation. The SRC will decide if another cohort of patients should be enrolled at a higher SQP33 protodrug dose with the same 20 mL SQL70 biopolymer volume.

See section [4.1 General Inclusion/Exclusion Criteria](#) for further details on the eligibility criteria for this cohort.

The 20 mL SQL70 biopolymer cohort described above is a unique and separate set of patients (see section [3.1.4.4 Phase 1: 20 mL SQL70 Biopolymer \(post-Cycle 1\) Cohort](#)).

3.2.4. Maximum Tolerated Dose

The MTD is defined as the dose level of SQP33 protodrug in which a total of 6 patients are treated at that dose level with ≥ 2 patients experiencing a DLT during Cycle 1 of treatment across all 6 patients. An SQP33 protodrug MTD may be determined for both groups the 10 mL and 20 mL doses of SQL70 biopolymer.

3.2.5. Recommended Phase 2 Dose

A determination of the RP2D will be based on the safety and tolerability from every cycle of treatment, not just Cycle 1. The RP2D will be determined based on all available data, including PK/PD analysis, tolerability that will include the incidence and severity of DLTs, other AEs and the evidence for biological activity at each dose level tested. The RP2D will be defined by an SQP33 protodrug dose and a SQL70 biopolymer volume.

3.2.6. Dose-Limiting Toxicity

AE and serious adverse event (SAE) severity is based on the National Cancer Institute Common Terminology Criteria for Adverse Events (NCI-CTCAE) v5.0.

A DLT is defined as an AE that is at least possibly related to study treatment, occurs during the patient's first cycle of treatment (21 days; also known as the DLT window), and is a:

- Hematologic toxicity
 - Febrile neutropenia
 - Grade ≥ 3 thrombocytopenia associated with clinically significant bleeding
 - Grade 4 neutropenia or thrombocytopenia lasting >7 days

or

- Grade ≥ 3 non-hematologic toxicity **except for:**
 - Grade ≥ 3 isolated asymptomatic laboratory abnormalities or laboratory abnormalities that resolve within 72 hours
 - Grade 3 nausea/vomiting/anorexia controlled by maximal medical management that does not persist for greater than 3 days
 - Grade 3 fatigue/asthenia that does not persist for more than 7 days
 - Grade 3 diarrhea or constipation that resolves to \leq Grade 1 or baseline within 72 hours with maximal medical management
 - Grade 3 or 4 elevation of amylase or lipase not associated with pancreatitis
 - Grade 3 infusion reaction returning to \leq Grade 1 in < 6 hours
 - Grade 3 tumor lysis syndrome that is successfully managed and resolves within 7 days without end-organ damage

Hepatic abnormalities that resolve within 7 days.

If a patient experiences a DLT, **both SQP33 protodrug and SQL70 biopolymer should be temporarily interrupted** (see section [7.6.3 SQ3370 Treatment Interruptions](#)). See section [3.1.5 End of Treatment](#) if discontinuation of Investigational Product is permanent.

3.2.7. Safety Review Committee (Dose Escalation and Phase 2a)

The SRC will include the study team led by the medial monitor, and the active Investigator(s). The SRC will review all available safety data at the completion of Cycle 1 for each cohort to evaluate possible DLTs, recommend whether more patients should be enrolled at a given dose level / cohort, and whether to dose escalate or to stop enrollment based on the definition of DLTs in addition to its members' best clinical judgement and will provide recommendations to the sponsor.

With agreement from the sponsor, the dose escalation scheme may be modified (e.g., smaller increases or decreases in dose may be permitted, infusion timing, duration, or schedule may be modified) based on available PK and pharmacodynamic data, and/or the timing and severity of AEs observed. Changes that can only be made with a protocol amendment will include:

- Dose level escalations that are increased by larger increments than the scheme in the protocol
- Administration of more than 5 SQP33 infusions per cycle
- Administration of more than 20 mL of SQL70 biopolymer per cycle

Phase 2a Responsibility

In Phase 2a, the SRC will utilize the same criteria to evaluate the safety and tolerability of all available safety data at the completion of timing for each group to determine the initial safety and monitor the groups throughout the study overall safety and tolerability.

Table 4: Phase 2a Safety Evaluation Timing

Group	Run-in Evaluation N= (timing)	Simon 2 Stage 1 evaluation	Final Assessment
1: Extremity STS	N=6 (after cycle 1)	N=15	N=46
2: STS unresectable	N=12 (6 per arm; after cycle 2)	N.A.	N=22
3a: Head and Neck	N.A.	N=13	N=26

N.A.= Not Applicable

A run-in is not planned for the Head & Neck group (Group 3a) since they will be receiving the RP2D and schedule of SQ3370 without modifications (see [Table 4](#)).

Group 1 will receive SLQ70 in a volume of 20 mL with the RP2D of SQP33 and therefore the safety lead-in to this group is warranted. The SRC may, after the planned initial review of any group, within its purview recommend additional monitoring to the sponsor.

[figure not shown]

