 - Patients will enroll at the RP2D of SQ3370. It is anticipated that the size of tumors given the stage and inclusion criteria eligible for enrollment will be potentially larger than in Phase 1, this group will receive a fixed dose of SQL70 (20 mL). All patients are planned to receive 2 cycles of SQ3370 and undergo a disease reevaluation per RECIST 1.1. All patients without evidence of disease progression after initial 2 cycles, will then undergo an additional 2 cycles of treatment and have a presurgical disease re-evaluation and proceed to definitive surgical procedure(s). (See [APPENDIX H – Schedule of Assessments – Expansion Group 1: Extremity STS](#) for details).
 - Only patients who have had objective evidence of response or whom in the opinion of the multidisciplinary treatment team determined to have achieved a clinical benefit may defer surgery at this point. Note that the study will allow up to 4 additional cycles, at which point all patients should undergo exploratory surgery and or tumor resection.
 - If a patient with Stage III had a radiological and surgical complete response (CR) they may receive up to 4 additional cycles, but no patient may exceed 12 cycles within the study. Stage IV patients may continue post op chemotherapy. Any patient group III or IV must have accessible lesions or the primary tumor that is deemed adequate for post operative intratumoral injection. If a patient receives post-operative radiation which is allowed on study, they meet End of Treatment criteria and will not receive further SQP3370 (see section [3.1.5 End of Treatment](#)).
 - Any patient at any point who has been determined to have progressive disease has reached end treatment and will proceed to a definitive surgical treatment, note pre-operative radiation is allowed for patients with progressive disease pre-operatively on study at this point.
 - Subjects will be treated with the RP2D of SQ3370 every 21 days (1 cycle) up to 12 cycles or until other treatment discontinuation criteria are met (see section [3.1.5 End of Treatment](#)). On Day 1 of each cycle, the subject will receive an injection of SQL70 biopolymer into the tumor (20 mL), followed by 5 days of SQP33 infusion starting 3 hours ± 30 min after the SQL70 biopolymer injection.

- Group 2: Unresectable STS locally advanced or metastatic.

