 - Patients will enroll at the RP2D of SQ3370, maintaining the total dose per cycle constant and compare 2 different infusion schedules a 3-day vs a standard 5-day schedule. The 3-day cycle will administer the same dose on Day 1 as the 5-day cycle and 2x the doses on days 2 and 3 of the cycle. (See [APPENDIX I – Schedule of Assessments – Expansion Group 2: Unresectable STS \(5 day\)](#) and [APPENDIX J – Schedule of Assessments – Expansion Group 2: Unresectable STS \(3 Day\)](#) for details).
 - Eleven (11) patients per group. Subjects will be treated with the RP2D of SQ3370 every 21 days (1 cycle) up to 12 cycles or until other treatment discontinuation criteria are met (see section [3.1.5 End of Treatment](#)). On Day 1 of each cycle, the subject will receive an injection of SQL70 biopolymer into the tumor (10 mL) followed by 3 or 5 days of SQP33 infusion starting 3 hours ± 30 min after the SQL70 biopolymer injection.
- Group 3a: Head and Neck
 - Patients with histologically or cytologically confirmed relapsed or metastatic squamous-cell carcinoma of the head and neck (R/M HNSCC), who have exhausted curative intent therapies or patients with distant metastases who may have received one or less chemotherapy regimen.
 - This will follow a Simon 2-stage design. Thirteen (13) patients will be initially treated with the RP2D of SQ3370 every 21 days (1 cycle) up to 12 cycles or until other treatment discontinuation criteria are met (see section [3.1.5 End of Treatment](#)). On Day 1 of each cycle, the patient will receive a 10 mL injection of the SQL70 biopolymer into the tumor, followed by five (5) days of SQP33 infusion starting 3 hours ± 30 min after the SQL70 biopolymer injection. If ≥ 4 patients have a response (CR or PR), then 13 additional patients will be enrolled. (See [APPENDIX K – Schedule of Assessments – Expansion Group 3A: Head and Neck](#) for details).

Sample Size

Phase 1: Dose Escalation: Sample size for the dose-escalation portion of the study is not predefined. Total enrollment will depend on the DLTs observed and number of escalation cohorts.

Phase 2a: Expansion Groups 1 and 3a will be utilizing a Simon 2-stage (optimal) design to determine sample size (see below) based on historical objective responses per indication. Expansion Group 2 will utilize the Continuous Reassessment Method (CRM) design.

Simon 2-Stage Optimal Design

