Patients will enroll at the RP2D of SQP33 given over 5 days and will receive a fixed dose of SQL70 (10 mL) on Day 1 of each cycle, except for patients with a secondary lymph node lesion. These patients may receive an additional 10 mL in that lesion for a total of 20 mL of SQL70 injection. All subjects will commence treatment with SQP33 within 3 hours ± 30 minutes.

Any patient at any point who has been determined to have progressive disease has reached the End of Treatment, any subject completing 12 cycles of treatment will have been deemed to have reached the end of treatment. See [Schedule of Assessments Appendix K](#).

Note: All patients in Phase 2a expansion groups who are no longer on treatment should begin Long Term Follow Up per the [Schedule of Assessments](#).

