4.2.3. Expansion Group 3a: Head and Neck

4.2.3.1. Inclusion Criteria

- 1. Patients with histologically or cytologically confirmed squamous-cell carcinoma of the head and neck (HNSCC) who meet any of the following
 - a. confirmed relapsed HNSCC

- b. metastatic at initial presentation HNSCC
- 2. Patients who may have received two or less systemic regimens (therapies include chemotherapy and/or immunotherapy)
- 3. Biopsy-confirmed squamous-cell carcinoma (SCC) of the oral cavity, oropharynx, supraglottic larynx, or hypopharynx (archived biopsies are allowed)
- 4. For participants with oropharyngeal cancer, human papilloma virus (HPV) p16 status must be documented at screening
- 5. Has at least 1 tumor lesion that can be accurately measured by CT or MRI according to RECIST 1.1 and is amenable for intratumoral injection, as determined by the Investigator
- 6. The primary tumor itself must be injected, if amenable for intratumoral injection, and must be noted at screening and targeted for intratumoral injection
 - a. A secondary lesion may be injected if, biopsy confirmed SCC that is eligible for intranodal injection*,
 - Secondary lesions may include metastasis eg, soft tissue mass or lymph node (LN) in the neck of ≥ 3 cm

*No lesion with 180-degree or more encasement of the carotid artery on MRI or CT scan may be selected

- 7. ECOG performance status of 0 to 2
- 8. Life expectancy ≥ 6 months

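### Group 3a is exempt from a safety run-in because its RP2D is unmodified, yet some of its patients may receive 20 mL of SQL70, the volume that justifies the Group 1 lead-in, with no SRC gate on that option

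*Protocol*

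**What the plan says.** Protocol section 3.2.7 (with Table 4) plans no run-in for Group 3a, "since they will be receiving the RP2D and schedule of SQ3370 without modifications". The first review listed for that group is at N=13. The next paragraph says that Group 1 will receive SQL70 "in a volume of 20 mL with the RP2D of SQP33 and therefore the safety lead-in to this group is warranted"; that run-in is six patients after Cycle 1. Section 7.1 of the Phase 2a SAP repeats both statements.

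Section 3.1.4.1 sets Group 3a at 10 mL but makes an exception where there is a second, nodal lesion. Of the patients concerned it says: "These patients may receive an additional 10 mL in that lesion for a total of 20 mL of SQL70 injection". Inclusion criterion 6a in section 4.2.3.1 is consistent with this: "A secondary lesion may be injected if, biopsy confirmed SCC that is eligible for intranodal injection".

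Section 3.2.5 defines what counts as the RP2D: "The RP2D will be defined by an SQP33 protodrug dose and a SQL70 biopolymer volume".

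Other places give Group 3a 10 mL with no exception. The Synopsis says "the patient will receive a 10 mL injection of the SQL70 biopolymer into the tumor". Protocol Table 1 and section 3.5.1, and Phase 2a SAP sections 2.1, 2.3 and 10.8, also list 10 mL only.

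**The concern.** By the protocol's own logic, 20 mL with the RP2D of SQP33 is a departure that calls for early review. A Group 3a patient who uses the secondary-node option gets that combination, possibly from Cycle 1, while belonging to a group excused from early review because nothing has been changed.

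Safety and tolerability is the primary Phase 2a objective. When 20 mL from Cycle 1 was introduced in Phase 1, it had separate cohorts and its own SRC step: "A per cohort SRC meeting will convene following the same guidelines as utilized for the SQP33 protodrug escalation". In Phase 2a the only early review tied to 20 mL is the Group 1 run-in, and no text links the Group 3a option to it. A reader of the Phase 2a SAP alone would not learn that the Group 3a option exists.

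**Working it through.** The plan states no figure on this point. The check is a comparison of text, followed by arithmetic on how often the option might be used.

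**1. Is 20 mL a modification for Group 3a?** Section 3.2.5 makes the RP2D a pair, SQP33 dose and SQL70 volume. Every regimen listing for Group 3a pairs the RP2D of SQP33 with 10 mL, so 20 mL changes one member of the pair. If 20 mL were instead counted as unmodified, the reason given in section 3.2.7 for the Group 1 lead-in would fall away. The two statements cannot both hold for a Group 3a patient given 20 mL.

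**2. What is known about 20 mL?** Protocol section 1.4 reports eight patients given 20 mL in the Phase 1 cohort, five at 4x and three at 6x Dox equivalent. Grade 3 or greater anemia was reported in 3 (3/8 = 37.5%) and neutropenia in 2 (2/8 = 25%). The Phase 2a SAP, a Version 0.1 draft, sets SQP33 at 250 mg/m² and calls it 12x. Reading 250 mg/m² as a daily dose, with the documents' conversion factor of 0.7153 and reference dose of 75 mg/m²:

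250 × 5 × 0.7153 / 75 = 11.9x, which agrees with 12x.

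Reported 20 mL-from-Cycle-1 experience therefore stops at half the planned SQP33 multiple (6x against 12x). Sections 3.1.1 and 3.1.4.4 also allowed a move to 20 mL after Cycle 1 in the 10 mL escalation; how many patients did so, and at what dose, is not reported.

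**3. How many Group 3a patients might receive 20 mL before the N=13 review?** Let p be the share of the group actually given 20 mL (eligible and chosen by the investigator). The documents do not give p; the values below are assumptions, and zero is possible.

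- Expected number among the first 13 = 13p
- P(at least one) = 1 − (1 − p)^13
- P(none) = (1 − p)^13

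| p (assumed) | Expected in first 13 | P(at least one) | P(none) |
|---|---|---|---|
| 5% | 0.65 | 49% | 51% |
| 10% | 1.3 | 75% | 25% |
| 25% | 3.25 | 98% | 2% |
| 50% | 6.5 | >99.9% | <0.1% |

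These figures count exposure, not harm. At p = 5% or 10%, the N=13 review has a 51% or 25% chance of containing no 20 mL patient at all.

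**4. Would a Group 1-style run-in of six unselected Group 3a patients close the gap?** P(none of six given 20 mL) = (1 − p)^6: 0.90^6 = 53% at p = 10%, and 0.95^6 = 74% at p = 5%. It would often miss the option altogether.

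**The case against.** The strongest case against runs as follows.

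- **Oversight exists before N=13.** Section 3.2.7 has the SRC monitor all groups throughout Phase 2a and lets it recommend additional monitoring. Safety is assessed continuously (section 8.3), SAEs and AESIs, including DLTs, are reported within 24 hours (sections 7.1.2 and 7.2), SQL70 can be cut from 20 to 10 mL and SQP33 by 25% (section 7.6.2), and the study can be interrupted at any time (section 3.4). A reader might infer that these patients go unmonitored until the thirteenth; the documents do not support that. What stands is narrower: no review is scheduled earlier for this exposure. The same safeguards cover Group 1, where the sponsor still required a lead-in, and the SQL70 volume reduction is worded for a 20 mL group, which does not clearly include these patients.
- **The exposures differ.** In Group 1, 20 mL is the fixed dose for everyone, and the run-in also tests a 12-week delay of surgery. In Group 3a it is optional, limited to a subset, and split as 10 mL in each of two lesions, a use explored in Phase 1 (section 3.5.2). All of this is correct. It limits the point to that subset, but section 3.2.7 names the volume as its reason for the lead-in.
- **The toxicity evidence is thin.** A reader might infer from section 1.4 that 20 mL is more myelosuppressive than 10 mL, since Grade 3 or greater anemia was 3 (37.5%) against 4 (16.7%). The comparison is small, non-randomized and across different SQP33 doses, so it does not show that. Nor can one infer that nobody has received 20 mL at 12x, because post-Cycle 1 use is unreported.
- **The subset may be empty.** True; no figure in the documents settles it.

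**Conclusion.** The point holds for Group 3a patients who receive the additional 10 mL. For them the stated ground for having no run-in is untrue, no scheduled SRC review before N=13 covers them, and the option does not wait for the Group 1 review. The textual conflict rests on no assumption beyond reading the Group 3a RP2D volume as 10 mL, as the regimen tables list it. The size does rest on assumption: between p = 5% and p = 50%, the chance of at least one such patient among the first 13 runs from 49% to above 99.9%, and p could be zero. The gap in experience (reported 20 mL from Cycle 1 only at 4x and 6x) relies on a draft SAP for the 12x figure.

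A reader might infer that Group 3a needs its own group-wide run-in. It does not: patients on 10 mL receive the regimen as listed, and such a run-in would often contain no 20 mL patient. The defect is an ungated optional volume and inaccurate wording. It should be fixed because it bears on the primary objective and costs little.

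**What to change.** In protocol section 3.2.7 and Table 4, and in Phase 2a SAP section 7.1, state that the additional 10 mL in Group 3a may not be given until the SRC has reviewed the Group 1 run-in (N=6 after Cycle 1). That review informs systemic tolerability of 20 mL with the RP2D of SQP33, but not local tolerability of two head and neck injections.

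If the wait is too long, let the SRC review the first Group 3a patient given 20 mL, after Cycle 1, before any other receives it. This also covers local tolerability. The review should start with the first such patient: waiting for three would take about 3/p enrolled, which is 30 at p = 10% and exceeds the 26 planned.

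Replace the claim of no modifications with wording that covers the exception. Align the Synopsis, Table 1 and section 3.5.1 of the protocol, and sections 2.1, 2.3 and 10.8 of the Phase 2a SAP, with section 3.1.4.1.

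Cost: either eligible patients stay on 10 mL until six Group 1 patients complete Cycle 1 (21 days after the sixth starts) and the SRC meets, with timing that depends on Group 1 accrual, which is not stated; or there is one extra SRC review. The gate is a change of dosing rule, so it goes through a protocol amendment with the approvals in section 11.2. It needs no extra patients and leaves the Simon boundaries unchanged.
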